### 5.2.3.2.1 Allowed Concomitant Therapy

Standard supportive care for drug-related toxicity is permitted, including growth factors and blood product transfusions per local institutional standards. Other standard supportive care for symptom control or drug-related toxicity is allowed, such as analgesics, anti-emetics, electrolyte replacement, and hydration. Bone modifying agents

(e.g., bisphosphonates, denosumab) for bone metastases are also permitted per local institutional standards. Other prescribed medications for non-neoplastic conditions are allowed, as well as vitamins and nutritional supplements.

[figure not shown]
Concomitant prednisone (or equivalent) may be used at a dose of  $\leq 10$  mg/day. The use of intermittent high-dose corticosteroid treatment to prevent or manage infusion reactions, serosal effusions (see Section 6.1.8.1), or other non-cancer-related symptoms including premedication for known hypersensitivity reactions to contrast for scans is allowed.

Routine prophylaxis with vaccines is permitted; however, vaccines used should not contain live micro-organisms.

If the subject is taking chronic suppressive anti-infectives (antiviral, antifungal, or antibacterial), appropriate investigation must be completed prior to randomization, and documentation must exclude active infection. After exclusion of active infection, otherwise eligible subjects should complete or continue suppressive anti-infectives as prescribed.

If a subject requires palliative radiation during the study (e.g., symptomatic worsening of a bone lesion) diagnostic imaging has to be performed to assess for radiographic progression prior to radiation, and documentation of non-progressive status by radiography will be captured in the eCRF. Any cancer-directed therapy a subject receives due to disease improvement should be discussed with the TA MD in advance, if possible.

In the event of isolated CNS-only progression during study treatment, blinded investigational product may be withheld while local treatment is administered (e.g., radiotherapy) in accordance with institutional practice. Blinded investigational product may be restarted 1 week after the completion of local CNS disease-directed therapy.

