#### **End of Treatment (EOT) Visit**

The visit at which an investigator identifies disease progression or a subject meets other criteria for study treatment discontinuation will be considered the End of Treatment Visit. The EOT procedures should be done within 7 days of documented decision to discontinue treatment and prior to subjects beginning any new anti-cancer therapy if possible. The

EOT visit is the last visit during the treatment phase before subjects begin the Post Treatment Follow Up and/or Survival Follow Up phase. The reason(s) for the discontinuation from study treatment will be recorded and assessments will be performed per Appendix C, Study Activities.

Disease/Response Assessment, CT/MRI of the brain (if applicable), and submission of scans to the CRAC, may be omitted if performed within the last 6 weeks.

[figure not shown]

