### 5.4 Removal of Subjects from Therapy or Assessment

Each subject has the right to withdraw from study treatment at any time. In addition, the Investigator may discontinue a subject from the study treatment at any time for any reason if the Investigator considers it necessary. Each subject will be withdrawn from the study or study treatment (as applicable) per Section 5.4.1 if any of the following occur:

- The subject has radiographic progression according to RECIST v1.1 (with the exception of CNS-only progression).
- The subject requires cancer-directed radiotherapy or surgery related to clinical disease progression, or alternate anti-cancer agents during the study period. (Refer to Section 5.2.3.2.1, Allowed Concomitant Therapy for exceptions from this criterion).
- The subject experiences treatment toxicity which, in the Investigator's opinion, prohibits further therapy or the Investigator believes it is otherwise in the best interest of the subject.
- Subject is pregnant or begins breastfeeding during the treatment portion of the study.
- The subject decides to withdraw consent for any reason.
- Any other medical reason that AbbVie or the study Investigator deems appropriate.
- Significant non-compliance to the protocol.

Discontinued subjects will not be replaced.

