### 5.4.1 Discontinuation of Individual Subjects

[figure not shown]
When subject discontinuation from study treatment (without reaching a protocol-defined endpoint) is planned, the Investigator is to notify the AbbVie Therapeutic Area Medical Director (TA MD) or the clinical team representative (Section 7.0) via telephone as soon as possible (provided, in each case, subject care and safety are not compromised). If not notified prior to discontinuation, the AbbVie TA MD may contact the site to discuss the reason for withdrawal from the study.

The visit at which an investigator identifies disease progression or a subject meets other criteria for study treatment discontinuation will be considered the End of Treatment Visit. The reason(s) for the discontinuation from study treatment will be recorded and assessments will be performed per Appendix C, Study Activities. It is preferable that End of Treatment Visit procedures be conducted prior to the initiation of another anti-cancer therapy. However, these procedures should not interfere with the initiation of any new treatments or therapeutic modalities that the Investigator feels are necessary to treat the subject's condition.

If a subject is discontinued with an ongoing adverse event or an unresolved clinically significant laboratory result, the site will attempt to provide follow-up until a satisfactory clinical resolution of the laboratory results or adverse event is achieved.

Subjects no longer undergoing clinical assessments will have survival information collected at every 6 weeks (± 1 week) until the endpoint of death, the subject becomes lost to follow-up or withdraws consent, or termination of the study by AbbVie, whichever occurs first.

In the event that a positive result is obtained on a pregnancy test for a subject during the study, the administration of blinded investigational product to that subject must be

discontinued immediately. The site must report the positive pregnancy test result by completing the appropriate eCRF within 24 hours of becoming aware of the pregnancy.

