10.1.1 Statistical Analysis Methods

Time-to-Event Endpoints

All time to event (TTE) endpoints are defined using a time variable and an event indicator. All TTE efficacy endpoints in this study are concerned with only the

first occurrence of the event of interest, all recurrence of the same event is not considered for endpoint derivation or analysis. An event however may be defined in a composite manner, i.e., as the occurrence of one among several different outcomes. The composite event is observed when at least one of the component events occurs, and the time to the earliest among the occurring component events is considered to be the TTE for the composite event.

The time variable will be computed in days and converted into months (1 month = 30.4375 days). Thus, for subjects who experience the event of interest, time to event will be defined as the time from randomization to the first occurrence of the event. When multiple assessments are needed to ascertain the occurrence of an event, the earliest date among all of these assessments is taken to be date of the event or censoring. For a subject who does not experience an event on the study, time will be right censored at the time of his last available adequate post-baseline assessment that rules out the occurrence of the event. If a subject had no post-baseline assessment and did not experience the event of interest, then TTE will be censored at the date of randomization and we will set TTE = 1 day, by convention.

Follow-up time for TTE endpoints will be derived as follows:

$$\text{TTE} = \text{Date of first occurrence of an event or censoring} - \text{date of randomization} + 1.$$

TTE endpoints will be summarized by number of events observed, number of subjects censored, and times corresponding to 25% (1st quartile), 50% (median) and 75% (3rd quartile) event probabilities. Kaplan-Meier (KM) estimates will be calculated and plotted. Comparison between treatment arms will be based on stratified log-rank tests as specified.

A Cox proportional-hazards regression model with the treatment group and stratification factors as covariates will be used to estimate the hazard ratio (HR) of rovalpituzumab tesirine to placebo and its two-sided 95% confidence interval (CI).^{2,3} Only the main effects of the stratification variables will be fitted.

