10.2 Efficacy Endpoints and Analyses

10.2.1 Primary Efficacy Endpoints

The primary efficacy endpoints are:

- Progression-free survival (PFS) determined by the CRAC
- Overall survival (OS)

Progression Free Survival (PFS)

PFS will be defined as the number of months from randomization to disease progression, as assessed by the CRAC per RECIST v1.1, or death of any cause, whichever occurs first. Any death that occurs > 12 weeks (two consecutive missing scans) after the previous radiographic disease assessment, or any PD or death happened after the initiation of new anti-cancer therapy will be excluded disregarded from the analysis. Subject without an event will be censored at the last date of post-baseline radiographic assessment. Subject with no post-baseline assessment and did not experience death event within 12 weeks of randomization will be censored at the date of randomization.

Differences between the treatment arm and the placebo arm in PFS will be assessed by a log-rank test stratified by the randomization stratification factors, testing the null hypothesis (rovalpituzumab tesirine arm is not superior to placebo arm in PFS). The hazard ratio of the treatment arm over the placebo arm will be calculated by a Cox's proportional hazards regression model adjusting for the main-effects of the stratification factors. Median PFS and 95% confidence intervals will be estimated using Kaplan-Meier survival methodology, with the Kaplan-Meier survival curves presented to provide a visual description. PFS rates at 3, 6, 9, and 12 months after randomization with 95% confidence intervals will be reported. Estimates of the treatment effect will be expressed as hazard ratio including 95% confidence intervals estimated through a Cox proportional-hazards regression model adjusting for the main-effects of the stratification factors. The same methodology will be applied to PFS based on investigator assessment.

Overall Survival (OS)

OS is defined as time from the randomization to death due to any cause. For subjects who are alive at the end of this study, OS will be right-censored on the last date the subject is known to be alive.

Differences between the treatment arm and the placebo arm in OS will be assessed by a log-rank test stratified by the randomization stratification factors, testing the null

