10.3 Sensitivity Analyses

Efficacy analyses for the primary endpoints (PFS per CRAC and OS) will be performed in the Per Protocol Set.

Two sensitivity analyses will be carried out for PFS endpoint by implementing different censoring rules in the definition of PFS (i.e., modified PFS endpoint). These sensitivity analyses will be conducted in either DLL3^{high} Set or Randomized Set.

Sensitivity analysis 1: PFS will be defined as the number of months from randomization to disease progression, as assessed by the CRAC per RECIST v1.1, or death of any cause, whichever occurs first. Subjects without an event will be right-censored at the date of last follow up for disease progression. Patients with no post baseline follow up for progression and who doesn't experience a death event will be censored at the day of randomization.

Sensitivity analysis 2: PFS will be defined as the number of months from randomization to disease progression, as assessed by the CRAC per RECIST v1.1, or death of any cause, whichever occurs first. Subjects with 2 or more consecutive missed assessments (i.e., > 12 weeks since last scan) without any subsequent assessment prior to the PFS

event (i.e., progression or death) will be considered progressed at the planned date of the earliest missed scan date (i.e., last scan date prior to event + 6 weeks). Subjects without an event or receives new anti-cancer therapy will be right-censored at the date of last follow up for disease progression.

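### The PFS rule disregards events after new anti-cancer therapy but does not limit the censoring date to scans before that therapy; as a minor separate point, per-protocol OS inherits a withdrawal-criterion censoring rule

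*SAP*

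**What the plan says.** **PFS.** SAP 10.2.1 (Progression Free Survival) states that "any PD or death happened after the initiation of new anti-cancer therapy will be excluded disregarded from the analysis". The next sentence gives the date: "Subject without an event will be censored at the last date of post-baseline radiographic assessment". It does not mention the start of new therapy.

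Three other places bear on that date:

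- SAP 10.1.1, for time-to-event endpoints generally: "time will be right censored at the time of his last available adequate post-baseline assessment that rules out the occurrence of the event". Adequacy is not defined, and new therapy is not mentioned.
- SAP 10.3, sensitivity analysis 2: "Subjects without an event or receives new anti-cancer therapy will be right-censored at the date of last follow up for disease progression". This names new therapy but does not tie the date to it.
- Protocol 8.1.4 refers PFS censoring to published conventions (reference 15) and writes out no new-therapy rule.

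**Scanning after treatment stops.** Protocol 5.3.1.1 (Post-Treatment Follow Up) and Appendix C note c end the visits at progression or new anti-cancer therapy, whichever is first. Protocol 5.3.1.1 (Disease/Response Assessment) continues 6-weekly tumor follow-up to progression, without that second stopping point.

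**Per-protocol OS.** SAP 5.0 censors per-protocol subjects who met a withdrawal criterion but were not withdrawn, from the time they met it. Protocol 5.4 lists RECIST progression, other than CNS-only, among those criteria. SAP 10.3 runs both PFS and OS in this set.

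**The concern.** If an event after new therapy cannot count, time after new therapy should not count as time at risk either. As written, a subject scanned after switching adds exposure during which an event is impossible. This lowers the apparent hazard in that subject's arm. If such subjects are unequally split between arms, the hazard ratio for a primary endpoint shifts towards favoring the arm that has more of them.

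The per-protocol point is separate and smaller. Progression predicts death, so censoring OS at progression is informative. A difference between the per-protocol and main OS results would then be hard to interpret.

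**Working it through.** **Plan figures.** The documents give no figure for this point. The PFS sizing reproduces: 4(2.807 + 1.341)²/(ln 0.667)² = 420 events for 91% power at one-sided 0.0025, with critical hazard ratio exp(−2 × 2.807/√420) = 0.760. The issue is the censoring date, not the sizing.

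**One subject under three readings.** SAP 10.1.1 sets time = date − randomization + 1, with 30.4375 days per month. Suppose stable disease at Week 6, new therapy at Week 8, stable disease at Week 12 and progression at Week 18. The progression is disregarded, so the subject is censored:

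| Reading | Scan used | Time |
|---|---|---|
| SAP 10.2.1 taken literally | Week 18 (the progression scan) | 127/30.4375 = 4.17 months |
| SAP 10.1.1 | Week 12 (last clean scan) | 85/30.4375 = 2.79 months |
| Last scan before new therapy | Week 6 | 43/30.4375 = 1.41 months |

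All three give zero events, so only exposure changes.

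**Can such scans exist?**

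- The Disease/Response Assessment text continues scans to progression, while Post-Treatment Follow Up and Appendix C stop visits at new therapy. Sites could follow either.
- End-of-treatment procedures come "prior to subjects beginning any new anti-cancer therapy if possible", and protocol 5.4.1 adds that "these procedures should not interfere with the initiation of any new treatments or therapeutic modalities". A scan shortly after new therapy is therefore possible.
- Protocol 5.2.3.2.1 provides for the case "If a subject requires palliative radiation during the study", and protocol 5.4 refers to "Allowed Concomitant Therapy for exceptions from this criterion". Such a subject may stay on treatment and keep the 6-weekly scans. If this radiation counts as new anti-cancer therapy, later scans arise by design. The SAP does not say whether it does.

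**Size, illustration only.** Assume exponential PFS and a share p of an arm scanned to progression after new therapy, unrelated to prognosis. Under the literal reading, events/exposure = hazard × (1 − p), so the hazard ratio is multiplied by (1 − p on rovalpituzumab tesirine)/(1 − p on placebo):

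- 3% vs 1%: 0.97/0.99 = 0.98
- 2% vs 5%: 0.98/0.95 = 1.03
- equal shares: 1.00

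These shares are assumed. Within this simple model, the factors are upper bounds on the shift for those shares, because SAP 10.1.1 would end follow-up earlier, at the last clean scan.

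**Per-protocol OS.** Suppose RECIST progression at Week 12, no withdrawal, and death at Week 36. The main OS analysis has an event at 253/30.4375 = 8.31 months. The per-protocol analysis censors at 85/30.4375 = 2.79 months.

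**The case against.** The strongest reply is that the protocol schedules almost no such scans. Visits end at new therapy, Appendix C shows no imaging in survival follow-up, other systemic anti-cancer therapy is prohibited on study (5.2.3.3), and a need for alternate agents is a reason for withdrawal (5.4). End-of-treatment procedures are due within 7 days of the decision to stop, and the scan may be omitted if one was done in the preceding 6 weeks. That route therefore adds little time. On this view, sensitivity analysis 2 is also less open than it looks, since follow-up for progression would itself end at new therapy. This stands as a reason to expect few affected subjects. It does not supply the missing limit, because the Disease/Response Assessment text says otherwise and the status of palliative radiation is open.

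A second reply is that the published conventions cited in protocol 8.1.4 may contain the limit. They may, and this review cannot see them. What can be said is that neither document writes the limit out.

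Third, SAP 10.1.1 prevents censoring on a scan that shows progression. That is right and makes the literal reading the less likely one, but a clean scan after new therapy still extends follow-up. Sensitivity analysis 1 counts every CRAC progression and death and so gives partial cover, though it answers a different question.

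On the per-protocol point, the rule is explicit, supportive only, and covers only subjects not withdrawn. Protocol 5.4 speaks of withdrawal from the study or study treatment. If stopping treatment counts as withdrawal, only subjects kept on treatment past a criterion are affected.

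**Conclusion.** The gap in the PFS censoring date is real and concerns a primary endpoint, but it is a wording gap with probably few affected subjects. Its effect on the hazard ratio is unknown in size and direction. It is zero if no scans follow new therapy. It is worth closing before unblinding because closing it costs almost nothing.

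The per-protocol OS point holds on the text as a minor matter: later deaths of the subjects concerned are informatively censored in that supportive analysis only.

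A reader might infer more than the documents support:

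- *That the PFS result is biased in a given direction, or loses power.* No switching or post-switch scanning shares are given, so neither can be claimed.
- *That the main OS analysis is affected.* SAP 10.2.1 censors OS only at the last date known alive.
- *That the per-protocol set should contain only DLL3-high subjects.* Protocol 8.1 and SAP 5.0 agree that it is drawn from all randomized subjects.

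**What to change.** - **SAP 10.2.1 and sensitivity analysis 2 in SAP 10.3:** censor subjects who start new anti-cancer therapy without a prior event at the last adequate CRAC scan on or before that start, or at randomization if there is none.
- **SAP:** state what counts as new anti-cancer therapy, including whether palliative radiation permitted under protocol 5.2.3.2.1 does.
- **Protocol 5.3.1.1 and Appendix C:** reconcile the Disease/Response Assessment text with Post-Treatment Follow Up and note c on whether tumor assessments continue after new therapy.
- **SAP 5.0 and 10.3:** do not apply the withdrawal-criterion censoring to OS.

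The cost is a few sentences and no new data; survival follow-up already collects the dates of subsequent therapies. PFS event counts do not change, because events after new therapy are already disregarded. The downside is slightly shorter censored PFS follow-up.

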10.2.2 Secondary Efficacy Endpoints

The secondary efficacy endpoints in Randomized Set are:

- OS
- PFS determined by the CRAC
- EORTC QLQ-C30 physical functioning domain

OS in the Randomized Set and PFS by CRAC in Randomized Set will be analyzed using similar statistical methods described for the primary endpoints.

Change from baseline of the items and domains of the EORTC QLQ-C30 physical functioning domain will be summarized by treatment arm. The treatment group differences will be evaluated by analyzing the change from baseline using the analysis of covariance (ANCOVA) model. Detailed scoring methods are provided in Section 10.2.3.

10.2.3 Exploratory Efficacy Endpoints

The exploratory efficacy endpoints in both DLL3^{high} Set and Randomized Set are:

- Objective Response Rate (ORR) per CRAC
- PFS per investigator assessment
- ORR per investigator assessment

- Clinical Benefit Rate (CBR) per CRAC and investigator assessment, respectively
- Duration of Response (DOR) per CRAC and investigator assessment, respectively
- Change from baseline in all PRO domains (except physical functioning) measured by EORTC QLQ-C30/LC13 and EQ-5D-5L.

Objective Response Rate (ORR)

ORR is defined as the proportion of patients with a best overall response (BOR) of confirmed complete response (CR) or confirmed partial response (PR) by CRAC review according to RECIST v1.1.

All subjects with measurable disease who were randomized regardless of whether they had any post-baseline assessment will be included in the analysis. Any subject who did not meet confirmed CR or PR criteria, including those who did not have post-baseline radiological assessments will be considered as non-responder.

ORR in treatment arms will be compared using Cochran-Mantel-Haenszel test stratified by randomization stratification factors. Rates and 95% confidence intervals will be reported for each treatment arm.

Similarly, analysis of ORR assessed by investigator will be performed.

Clinical Benefit Rate (CBR)

CBR is defined as the proportion of patients with a BOR of CR or PR, or stable disease (SD) by CRAC review according to RECIST v1.1.

All subjects with measurable disease who were randomized regardless of whether they had any post-baseline assessment will be included in the analysis. Any subject who did not meet CR, PR, or SD criteria, including those who did not have post-baseline radiological assessments will be considered as having no clinical benefit.

The same methodology as for the analysis of ORR will be applied. Similarly, analysis of CBR assessed by investigator will be performed as well.

Similarly, analysis of CBR assessed by investigator will be performed.

Duration of Response (DOR)

The duration of response (DOR) for a given subject will be defined as the number of months from the day the criteria are met for confirmed complete response (CR) or partial response (PR) by CRAC (whichever is recorded first) to the date of progressive disease or death, whichever occurs first. If a subject is still responding (i.e., has not progressed nor died after CR or PR), then the subject's data will be censored at date of the last radiographic assessment by CRAC. For subjects who never experienced CR or PR, these subjects' data will not be included in the DOR analysis. Distribution of the DOR will be estimated for each treatment arm using Kaplan-Meier methodology. Median DOR with corresponding 95% CI for each treatment arm will be provided.

The same methodology will be applied to analysis of the duration of response per investigator assessment.

Patients Reported Outcomes (PRO)

PRO assessments are performed at screening, Cycle 2 Day 1 only, the first Non-Treatment cycle, end of treatment (EOT), and post-treatment follow-up visits (if applicable). The EORTC QLQ-C30/LC13 scoring manual will be used to transform the raw scores into the domain scores (global health, functional scales, symptom scales/items). Change from baseline of the items and domains of the EORTC QLQ-C30/LC13 will be summarized by treatment arm. The EQ-5D-5L manual and the published weights will be used to convert the individual items to the utility scores. Change from baseline of the EQ-5D-5L utility score and VAS will be summarized by treatment arm. The treatment group differences will be evaluated by analyzing the change from baseline using the analysis of covariance (ANCOVA) model.

The EORTC QLQ-C30 is composed of global health status/QoL scale; five functional scales (physical, role, emotional, cognitive, and social); three symptom scales (fatigue, nausea and vomiting, and pain); and six single items (dyspnea, insomnia, appetite loss, constipation, diarrhea, and financial difficulties).⁴

EORTC QLQ-C30	Item (Question) Numbers	Item Range*
Global health status/QoL		
Global health status/QoL	29, 30	6
Functional scales		
Physical functioning	1, 2, 3, 4, 5	3
Role functioning	6, 7	3
Emotional functioning	21, 22, 23, 24	3
Cognitive functioning	20, 25	3
Social functioning	26, 27	3
Symptom scales/Items		
Fatigue	10, 12, 18	3
Nausea and vomiting	14, 15	3
Pain	9, 19	3
Dyspnea	8	3
Insomnia	11	3
Appetite loss	13	3
Constipation	16	3
Diarrhea	17	3
Financial difficulties	28	

* Item range is the difference between the possible maximum and the minimum responses to individual items; most items take values from 1 to 4, giving range = 3.

The lung cancer module (QLQ-LC13) is meant for use among lung cancer subjects in parallel with the core QLQ-C30. It is composed of one multi-item scale to assess dyspnea, and a series of single items assessing coughing, sore mouth, dysphagia, peripheral neuropathy, alopecia, hemoptysis, and pain.

QLQ-LC13	Item (Question) Numbers	Item Range*
Symptom scales/items		
Dyspnea	3, 4, 5	3
Coughing	1	3
Hemoptysis	2	3
Sore mouth	6	3
Dysphagia	7	3
Peripheral neuropathy	8	3
Alopecia	9	3
Pain in chest	10	3
Pain in arm or shoulder	11	3
Pain in other parts	12	3
Pain medication	13	3

* Item range is the difference between the possible maximum and the minimum responses to individual items.

All scales and single items are reported on categorical responses and will be linearly converted to 0 through 100 numeric values. Given a scale, the raw score (RS) is computed as the mean of component items over the number of items answered for that scale. Then the scale score (SS) will be computed as following.

For Global health status/QoL, and Symptom scales/Items,

$$SS = \{(RS - 1)/range\} \cdot 100.$$

For Functional scales,

$$SS = \{1 - (RS - 1)/range\} \cdot 100.$$

If 50% or more of the items are answered for a given scale, the scale score will be computed as described above. If not, the scale score will not be computed. For example, physical functioning contains 5 items (questions 1 through 5), and the scale score is calculated if at least 3 of the items are answered. For single-item measures (dyspnea, insomnia, appetite loss, constipation, diarrhea, and financial difficulties), none of the

single-item measures can be computed if not answered. If a scale score cannot be computed, the outcome for that score is left blank.

The scoring approach for the QLQ-LC13 is identical in principle to that for the symptom scales/single items of the EORTC QLQ-C30.

For each scale, the treatment group differences will be evaluated by analyzing the change from baseline each of the post-baseline assessments and to the final measurement (last PRO assessment per subject) using the analysis of covariance (ANCOVA) model. Simple summary statistics for QoL assessments at each timepoint will also be presented.

Changes in QoL scores at the scale level or at the domain level per time point will be evaluated by classifying them according to the 10-point change threshold into 3 categories:⁵

- Improved is defined as a 10 point or more improvement (i.e., increase for functional scales and decrease for symptom scales) from baseline.
- Stable is defined as a less than 10 point change from baseline.
- Deteriorated is defined as a 10 point or more deterioration (i.e., decrease for functional scales and increase for symptom scales) from baseline. Subjects without a valid QoL outcome will be considered as having deteriorated.

The EuroQol 5 Dimensions 5 Level (EQ-5D-5L) is a preference based measure of health status that consists of EQ-5D descriptive system and EQ visual analogue scale (VAS).

The EQ-5D descriptive system comprises the following 5 dimensions: mobility, self-care, usual activities, pain/discomfort, and anxiety/depression. Each of the dimensions is divided into 5 levels of perceived problems: Level 1 (indicating no problem), Level 2 (indicating slight problems), Level 3 (indicating moderate problems), Level 4 (indicating severe problems), and Level 5 (indicating extreme problems). EQ-5D-5L health status, defined by the EQ-5D-5L descriptive system, will be converted into a single preference – weighted health status or "utility" index score by applying country-specific weights (if

available) or U.S. weights (if not available). If country is not available in the look-up table, then weights based on the United States will be applied.

The EQ VAS records the respondent's self-rated health on a visual analogue scale (0 to 100). The VAS score will be measured separately.

The analyses will be performed in the DLL3^{high} and randomized sets. Mean change from baseline in EQ-5D-5L "utility" index score to each applicable post-baseline time point, and to the final measurement will be presented by treatment arm. The treatment group difference will be evaluated by analyzing the change from baseline using the analysis of covariance (ANCOVA) model. The same methodology will apply to the mean change from baseline in VAS score.

